8.1.2 Endobronchial Brushing

Endobronchial brushing samples will be collected from study participants during their bronchoscopy procedure using an endoscopic cytobrush (Cellebrity Endoscopic Cytobrush; Boston Scientific, Boston, MA) to collect normal appearing bronchial epithelial cells by rubbing against the bronchial wall. The bronchial brushings will be targeted to normal appearing epithelial tissue of the right main-stem bronchus and avoid sampling tumor tissue or dysplastic cells. If any abnormalities are observed on the right bronchus, the bronchial brushing samples will be collected from the left main-stem bronchus. Up to 4 bronchial brushing samples will be collected from each patient pre and post treatment, respectively. All brushing samples will be stored in an RNA preservative (RNAProtect; Qiagen) and sent to the test laboratory.

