5.5 Clinical Visits

Besides two clinical visits in stage 1 of the study for eligibility screening, all eligibility study participants will begin taking the study tablets at visit 1 of stage 2 of the study and return to the study clinic at the end of months 3, 6, 9, and 12 (the end of treatment period). At each clinical visit, the clinical research nurse/assistant will conduct the following:

- 1) Exam the subject's diary for dosing and timing of intake of test tablets, and keep the diary in subject's folder.
- 2) Count and record the remaining tablets given.
- 3) Provide new study tablets that will supply the next 3 months.
- 4) Study participant will turn in the self-administered questionnaire for recording his/her intake of cruciferous vegetables in the past 3 months using a dietary frequency questionnaire (Appendix 5).
- 5) Collect blood, spot urine and nasal brushing samples
- 6) Conduct pulmonary function test: FEV1/FVC
- 7) Collect safety and toxicity measures at each clinical visit (once every 3 months) during the 12-month treatment period:
 - a) Collect adverse events (AEs) using the AE Recording Form (Appendix 8)

- b) Conduct physical examination including body weigh, height, and vitals by a registered nurse and record the results in the patient's study file
- c) Laboratory evaluation: CBC with platelets and differential, chemistry panel including liver function testing.
- 8) Only at the end of treatment period, bronchoscopy will be performed on the patient using the same procedure as described above in 5.1(8) and bronchial biopsies and lavage samples collected (stage 2- visit 5).

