8. BIOSPECIMENS, BIOMARKER, AND SPECIAL STUDIES

8.1 Human Biospecimen Collection

8.1.1 Endobronchial Biopsies

Endobronchial biopsy samples will be collected during bronchoscopies. The procedure will be carried out by [name] (Co-PI) using Narrow Band Imaging (NBI) white-light bronchoscopy. Up to 3 biopsies will be taken from each of six predetermined sites: upper lobe orifices and superior segment orifices (left and right), carina between left upper lobe division and lingular orifices and right middle lobe orifice. In addition, biopsies will be taken from any sites that appear suspicious. On the post-treatment bronchoscopy, sites that had a mild or greater grade of dysplasia at baseline will be re-biopsied.

Of the 3 tissue blocks per biopsy site. All biopsy samples will be put in an ice-cooled box and sent to [name] (Co-I) for processing. Bronchial biopsies will be fixed in 10% neutral-buffered formalin for 6 to 24 hours, embedded in paraffin and routinely processed in the CLIA/CAP certified histology laboratory at the Department of Anatomic Pathology. One section per tissue block will be processed for routine hematoxylin-eosin (H&E) staining for histological evaluation and 10 unstained slides will be cut for immunoperoxidase studies.

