9.1 Statistical Analysis for histological responses

Endobronchial histology scores will be first summarized within each bronchoscopy by using 3 separate endpoint measures pre and post treatment respectively: 1) dysplasia index (DI, number of biopsies with dysplasia/total number of biopsies x 100), 2) average of all histological scores (all biopsies scores/number of biopsies), and 3) worst biopsy score. The 3 summary end points will be analyzed within 4 different biopsy site groupings: all biopsies, biopsies from the 6 standard endobronchial sites only, site-matched biopsies from both bronchoscopies, and site-matched biopsies where the baseline biopsy is non-normal. For each patient, the mean of each of endpoints separately for each of biopsy site groupings pre and post treatment are then calculated. The primary endpoint is the dysplasia index (DI), which has a binomial distribution with at least 6 “trials” (i.e., 6 predetermined biopsy sites), and will be analyzed by generalized estimating equations (GEE) that constrains average baseline DI to be the same for both treatment and placebo groups, and tests whether average follow-up DI differs between the SF treatment and placebo groups. All other endpoints and biopsy site groupings are secondary endpoints. The primary analysis for the average and worst dysplasia scores will be a linear regression that assesses the difference in post-treatment scores by the two treatment groups, controlling for the same scores at pre-treatment. This analysis of covariance (ANCOVA) approach has optimal efficiency in a study design to assess the pre- and post-treatment measures with high within-subject correlation due to repeated measures (80). No interim analyses for futility or superiority will be performed, other than ongoing safety monitoring.

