9.3 Statistical Analysis for Gene Expression

A summary gene expression score will be derived from previously determined gene expression features of 23 genes (19,82): $\text{score} = e^y / (1 + e^y)$, where $y = b_0 + \sum b_j * x_j$, where b_0 is the intercept, b_j is the coefficient, and x_j is the feature of the gene j expression [see details in (82)]. We will calculate the gene expression score (0~1) for each subject pre and post treatment separately. A linear mixed effect model will be used to assess the effect of SF on post-treatment gene expression scores, similar as described in Section 4.2.1. A decreased gene expression score post-treatment towards those seen in bronchial benign disease is indicative of the chemopreventive effect of SF on the lung cancer-gene expression.

We will use the similar approach to calculate a summary gene expression score of the 280-gene signature in bronchial premalignant lesions (PMLs) in identified our preliminary study. Similarly a linear mixed effect model will be used to assess the post-treatment gene expression scores. If SF causes a significant change of the score towards the regression of PMLs based on histological dysplasia index score, the gene-level expression changes will be examined to estimate the SF-treatment effects on individual gene or a cluster of genes.

To assess the similarity and difference in the gene expressions between the bronchial airway and nasal epithelia, we will use our similar methodologies described previously (73). For each gene identified in the analysis above, we will use a linear mixed effects model that includes site (bronchus or nose) and treatment (SF or placebo) as fixed effect. The regression model is given: $G_{ij} \sim \mu + \beta_s \cdot X_s + \beta_t \cdot X_t + \beta_{st} \cdot X_s \cdot X_t + \varepsilon_{ij}$, where G_{ij} is the \log_2 expression value for gene i in patient j ; the parameter μ is the overall mean of \log_2 fold change in gene expression, β_s and β_t for the respective site- and treatment-specific effect, and β_{st} for the interaction between site and treatment; and X_s for site (1=nose, 0=bronchus) and X_t for treatment (1=SF, 0=placebo).

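### Section 8.1.2 does not tie the month-12 brushing side to the baseline side, so some pre-post expression pairs can come from opposite main-stem bronchi

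*Combined protocol and SAP*

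**What the plan says.** Section 8.1.2 sets the default site and its purpose: "The bronchial brushings will be targeted to normal appearing epithelial tissue of the right main-stem bronchus and avoid sampling tumor tissue or dysplastic cells". It then gives the exception: "If any abnormalities are observed on the right bronchus, the bronchial brushing samples will be collected from the left main-stem bronchus". The rule covers both bronchoscopies: "Up to 4 bronchial brushing samples will be collected from each patient pre and post treatment, respectively".

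Section 5.5, item 8, has the month-12 bronchoscopy follow the procedure of section 5.1, item 8. Neither item mentions the side of brushing.

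Section 9.3 uses the brushings for the 23-gene score: "We will calculate the gene expression score (0~1) for each subject pre and post treatment separately". A 280-gene score is built in a similar way. The only site term in the section 9.3 models separates nose from bronchus; there is none for left versus right.

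Other samples are handled differently. For biopsies, section 8.1.1 fixes six sites in advance and adds: "On the post-treatment bronchoscopy, sites that had a mild or greater grade of dysplasia at baseline will be re-biopsied". Section 9.1 plans an analysis of "site-matched biopsies from both bronchoscopies". Nasal brushings (section 8.1.4) are taken from both sides.

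**The concern.** The side depends on what the bronchoscopist sees on the day. Read as written, the rule is applied again at month 12 without reference to baseline. A subject brushed on the left at baseline because the right looked abnormal moves to the right at month 12 once the right looks normal, even if the left still looks normal and could have been brushed again.

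In such a subject, the pre-post change in expression includes any difference between the two main-stem bronchi. That is noise in the comparison of changes between arms. The plan also hypothesises that sulforaphane (SF) improves the bronchial epithelium, so the month-12 side is a post-randomisation variable that could in principle differ between arms. At stake are secondary aims 1.2.1 and 1.2.2, and the bronchial half of aim 1.2.3. The primary dysplasia-index analysis does not use the brushings.

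**Working it through.** **Step 1. What the rule does.** Cross the reading of the right bronchus at the two bronchoscopies:

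| Right at baseline | Right at month 12 | Sides brushed |
|---|---|---|
| normal | normal | right, right |
| normal | abnormal | right, left |
| abnormal | normal | left, right |
| abnormal | abnormal | left, left |

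A mismatch needs a changed reading, through true change or inconsistent visual judgement. A right bronchus that looks abnormal both times gives a matched left-left pair.

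**Step 2. Reproduce the plan's power.** Inputs from section 9.3: 30 per group, effect d = 1.0 log2, SD of the pre-post difference 0.7, FDR 0.05, and a share of non-differential genes (pi0) of 0.999, 0.990 or 0.950. The Liu-Hwang method finds the cut-off c at which

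P(|T| > c under the null) / P(|T| > c under the alternative) = [0.05/0.95] × [(1 − pi0)/pi0].

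For two samples, df = 58 and the noncentrality is (1.0/0.7) × √(30/2) = 5.53.

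| pi0 | Stated power | Reproduced |
|---|---|---|
| 0.999 | 85% | 85.4% (c = 4.41) |
| 0.990 | 96% | 96.1% |
| 0.950 | 99% | 99.0% |

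A one-sample paired calculation with n = 30 gives 99.6% at pi0 = 0.999 and does not match. The stated power is therefore for a between-arm comparison of changes with SD 0.7, and 0.7 is the SD that side-switching would inflate. The plan's figures are correct on their own inputs.

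**Step 3. Noise, under assumptions.** Let a fraction q of subjects switch side, and let their change gain an extra, independent SD of tau (log2). The documents give neither value. The variance of the change becomes 0.49 + q × tau². For example, q = 0.20 and tau = 0.35 give 0.49 + 0.20 × 0.1225 = 0.5145. Power at pi0 = 0.999, against 85.4% with no switching:

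| q | tau = 0.35 | tau = 0.70 | tau = 1.0 |
|---|---|---|---|
| 10% | 83.8% | 78.6% | 70.9% |
| 20% | 82.1% | 71.2% | 55.3% |
| 30% | 80.4% | 63.5% | 41.1% |

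The larger losses need a left-right component as variable as the whole planned change, or more so (tau of 0.70 or above). With tau near zero the loss vanishes. The table is for a single gene on the log2 scale; it does not carry over directly to the 23-gene score, which runs from 0 to 1.

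**Step 4. Bias, under assumptions.** Bias = (difference between arms in net left-to-right switching) × (mean left-right difference in expression). With 10 to 30 points and 0.1 to 0.5 log2, it runs from 0.10 × 0.1 = 0.01 to 0.30 × 0.5 = 0.15 log2, against a planned effect of 1.0. The upper end needs both extreme values at once.

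**The case against.** The strongest defence is that the rule has a purpose: it keeps the sampled tissue normal-appearing. Section 8.2.4 describes the 23-gene marker as taken from a normal-appearing main-stem bronchus without naming a side, and its field-of-injury premise treats the whole airway, even the nose, as sharing the smoking response. If that holds, left and right should be close to interchangeable. The same rule applies in both blinded arms, and the aims are exploratory. That the side is chosen anew at month 12 is also an inference from a silent text.

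Most of this stands, and it limits the importance of the point. It does not remove it. Brushing the baseline side again when it looks normal serves the same purpose. The plan offers no left-versus-right data, and no text has the side recorded so that the premise could be checked.

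Four stronger readings are tempting, but the documents do not support them:

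- **A mismatch rate taken from the dysplasia index (DI).** A reader might use the planned 22% and 11% from section 9.1 as the chance that the right bronchus looks abnormal. DI is the share of biopsies with microscopic dysplasia, and none of the six predetermined sites is a main-stem bronchus. The brushing rule turns on visual appearance, for which no rate is given.
- **Switchers carry most of the information.** The section 9.3 score models use all subjects, and nothing weights them by visible airway change.
- **A confounded link to histology.** Section 9.3 mentions a "change of the score towards the regression of PMLs based on histological dysplasia index score", but as a direction that triggers gene-level examination. No model regresses score change on histological change.
- **A biased treatment effect.** Step 4 makes a material bias unlikely.

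**Conclusion.** The gap is real and small in scope. As written, section 8.1.2 allows pre-post expression pairs from opposite main-stem bronchi when the reading of the right bronchus changes, and section 9.3 has no means of seeing this. The consequence is avoidable noise in secondary, exploratory comparisons. Its size cannot be determined from the documents: the power figures above rest on assumed switch rates and an assumed left-right variance, and the loss may be small for the reasons given in section 8.2.4. Any bias between arms is likely negligible against 1.0 log2. The point is a nearly free improvement to a stated rule, not an error in the plan's calculations.

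**What to change.** In section 8.1.2, state that at month 12 the side brushed at baseline is brushed again whenever it looks normal, and that the other side is used only if it does not. Record the side at both bronchoscopies. This removes the left-to-right switches in which the left still looks normal. Switches forced because the baseline side has become abnormal will remain.

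In section 9.3, keep the main models unchanged. Side should not become a covariate in them, because the month-12 side is determined after randomisation. Add one sensitivity analysis, either restricted to same-side pairs or with a side-change term, and label it as conditioning on a post-randomisation variable. If some bronchoscopies have already been done, look for the side in the procedure records.

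The cost is protocol wording, one recorded field and one sensitivity analysis, with no extra brushing or assay. Splitting the baseline brushings between the two bronchi would make more same-side pairs available, but it leaves fewer per side and is not needed for this change.

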8.1.3 Bronchoalveolar Lavage

After the completion of bronchial biopsies and brushing, the bronchoscope will be wedged in the right middle lobe or lingular orifice. Up to 150 ml sterile saline will be instilled, retrieved by gentle suction. Percent recovery will be recorded. Recovered fluid will be passed through a micron sterile nylon filter (Becton Dickinson, New Jersey) to remove mucus and particulates, and pooled, and centrifuged. The BAL fluid will be harvested, aliquoted, and stored at -80°C for analysis later.

8.1.4 Nasal Epithelia

Nasal brushings will be collected during clinical visits at month 0 3, 6, 9 and 12 after randomization. A nasal speculum (Bionox, Toledo, OH) then spread the nare while a standard cytology brush is inserted underneath the inferior nasal turbinate. The brush is rotated in place for 3 seconds, removed, and immediately placed in 1 ml RNA Later (Qiagen). Brushings will be obtained from the right and left inferior turbinates as previously described (73).

8.1.5 Blood

Besides a blood sample for eligibility screening or toxicity testing (10 ml), an additional blood sample (70 ml) will be collected from study participants at months 0, 3, 6, 9, and 12 after randomization. Different blood components (serum, plasma, buffy coat, RNA) in blood samples will be separated and properly stored.

8.1.6 Urine

Spot urine samples will be collected at initial screening visit (for pregnancy test for women younger than 60 years). Similarly, spot urine samples will be collected as at months 0, 3, 6, 9, and 12 after randomization. Aliquots of collected urine samples will be stored at -80°C. The urine samples will be used for quantification of total ITC (dietary intake of cruciferous vegetables) and SF-NAC (for monitoring intake of SF tablets).

8.1.7 Creation of a Biospecimen Repository

Blood and urine are collected for future research that may include genetic analyses in the study. The Tissue Distribution Committee of the SF trial study is responsible for authorizing the distribution of stored DNA, serum, and urine and the determination of appropriateness of the proposed research which may include genetic analyses. This committee will review requests for the use of stored DNA, serum and urine, and provide samples to investigators if the project is scientifically and ethically acceptable. Patient samples will be provided to investigators with only the study identification number so that investigators will not know the patient's identity; thus enhancing patient confidentiality. Inadvertent discovery of non-parentage is not possible as we are only planning to collect blood from participants and not their family members. Examples of the types of genetic testing include polymorphisms in metabolizing enzymes such as GST genes. None of these genetic "susceptibility" factors would be sufficient to cause lung cancer, but they may interact with environmental exposures (such as tobacco smoke). Since this genetic testing will be performed at an unspecified time in the future, it is not possible to say that we will provide patients with any information regarding their genetic background. In the unlikely scenario that we do discover a significant gene that is clinically meaningful, we would make every attempt to contact patients with this information.

8.1.8 Identifiers

The participant's unique study ID number will be the only identifier on every specimen. Specimens will be stored in a locked -80°C freezer in the research laboratory at the UPMC Hillman Cancer Center.

8.2 Biomarkers

8.2.1 Histology (atypia)

It has long been established that abnormal bronchial histology (atypia) is associated with cigarette smoking and increased risk for lung cancer. In a follow-up study of a high-risk cohort of subjects with endoscopic biopsies, persistence of bronchial dysplasia was associated significantly with a 7-fold increased risk of developing NSCLC (adjusted hazard ratio = 7.8, 95% CI 1.6-39.4) (18). All bronchial biopsies

for histopathological evaluation will be formalin fixed, paraffin embedded, and H&E stained for subsequent morphologic evaluation and classification. Biopsies will be classified into 1 of 8 categories as defined by the World Health Organization (WHO) classification (74) and assigned a score according to the following system: 1= normal; 2= reserve cell hyperplasia; 3 = squamous metaplasia; 4 = mild dysplasia; 5 = moderate dysplasia; 6 = severe dysplasia; 7 = carcinoma in situ; and 8 = invasive carcinoma. Subjects with baseline score 7 or 8 are ineligible for the proposed study. All biopsies will be graded by the study pathologist ([name]) in a blinded fashion as to treatment group.

Endobronchial histology scores will be first summarized within each bronchoscopy by using 3 separate endpoint measures pre and post treatment respectively: (1) The first endpoint measure is dysplasia index (DI), that solely examines changes in dysplasia pre and post-treatment. The number of biopsies with dysplasia (with WHO histology classification score: 4-6) are divided by the total number of biopsies and multiplied by 100. A positive change of 10% or greater indicates progression while a negative change of 10% or greater is regarded as a positive response. Scores in-between are coded as stable. (2) The second endpoint measure is the mean histological scores. It is calculated by adding the scores from all the biopsy sites and determining the mean value pre and post-treatment. A positive change in the score by 1 or more points is defined as progressive disease, a negative change in the score by 1 point or more points is defined as a partial or complete response and scores in-between are defined as stable disease. (3) The third model is called the “worst score”. It identifies the worst histological grade pre- and post- treatment. A positive change in the score by 1 or more points is defined as progressive disease, a negative change in the score by 1 point or more points is defined as a partial or complete response and scores in-between are defined as stable disease. The final response determination for a patient requires the same response determination in 2 of the 3 measures. For the rare patient with a different response for each category (progression, stable and response) the patient will be deemed stable. These summary scores will be created by the study statistician with the input of all investigators, in particular [name].

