8.3 End of Treatment Evaluation

8.3.1 Histological Response

Histology on bronchial biopsies pre-treatment and post-treatment will be compared. All biopsies will be graded according to the WHO classification for bronchial epithelium (74):

WHO Classification	Grade
Normal	1.0
Reserve Cell Hyperplasia	2.0
Metaplasia	3.0
Mild Dysplasia	4.0
Moderate Dysplasia	5.0
Severe Dysplasia	6.0
Carcinoma in Situ	7.0
Carcinoma	8.0

Response will then be determined by three scoring methods:

- a) The worst histology grade per patient pre and post treatment.

Worse = \geq 1 point higher post treatment

Better = \geq 1 point lower post treatment

Same = same point score pre and post treatment

- b) Average histology (all biopsies scores/number of biopsies) pre and post treatment

Worse = \geq 1 point higher post treatment

Better = \geq 1 point lower post treatment

Same = same point score pre and post treatment

c) Dysplasia index (number of biopsies with dysplasia/total number of biopsies x 100) pre and post treatment.

Worse = $\geq 10\%$ higher post treatment

Better = $\geq 10\%$ lower post treatment

Same = $< 10\%$ difference post treatment

The final response determination will require the same response parameter (worse, better or the same) for 2 of the 3 methods.

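### The primary dysplasia index counts only scores 4-6, so a follow-up biopsy read as carcinoma in situ (7) or invasive carcinoma (8) is scored as free of dysplasia

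*Combined protocol and SAP*

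**What the plan says.** Section 8.2.1 grades each biopsy on an eight-point scale whose top two categories are given as "7 = carcinoma in situ; and 8 = invasive carcinoma". It excludes these at entry only: "Subjects with baseline score 7 or 8 are ineligible for the proposed study". The DI is then defined: "The number of biopsies with dysplasia (with WHO histology classification score: 4-6) are divided by the total number of biopsies and multiplied by 100". On change from baseline, "a negative change of 10% or greater is regarded as a positive response".

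Section 8.3.1(c) restates the index without a score range: "Dysplasia index (number of biopsies with dysplasia/total number of biopsies x 100) pre and post treatment". Section 9.1 does the same, makes the DI the primary endpoint, and tests by GEE whether mean follow-up DI differs between the arms. Mean and worst scores are secondary. Neither section brings scores 7 and 8 into the numerator.

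Section 8.3.1 also sets a patient-level response: "The final response determination will require the same response parameter (worse, better or the same) for 2 of the 3 methods". Section 8.2.1 adds that a patient whose three measures all disagree is called stable.

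On sampling, section 8.1.1 says "Up to 3 biopsies will be taken from each of six predetermined sites", and that after treatment "sites that had a mild or greater grade of dysplasia at baseline will be re-biopsied".

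**The concern.** Scores 7 and 8 can appear only after baseline, and the DI has no place for them. Two kinds of progression are misread. A biopsy that goes from 4-6 to 7-8 leaves the numerator, as if it had become normal. A biopsy that goes from 1-3 to 7-8 registers no change. In the primary GEE, which compares follow-up DI, both are coded the same as normal tissue.

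The first kind is within reach of the design. Severe dysplasia is eligible under section 3.1, and dysplastic sites must be re-biopsied. Section 5.1 says the purpose of that re-biopsy is to see whether the lesions progressed or regressed. At the step from severe dysplasia to carcinoma in situ, the primary endpoint of a cancer-prevention trial reports the wrong direction. If one arm had more such readings, that arm would look better on the primary test.

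**Working it through.** **Inputs.** Numerator 4-6 and denominator all biopsies (8.2.1). Response cuts of 10 for the DI and 1 point for the mean and worst scores (8.2.1), with the 10% read as percentage points. 60 completers, taken as 30 per arm; 6 biopsies each; baseline DI 22%, post-therapy DI 11% on SF; two-sided 0.05; 80% power (9.1). The placebo follow-up DI is not stated and is taken as 22%.

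**The plan's own figure.** Comparing 22% with 11% on 30 x 6 = 180 biopsies per arm, treated as independent, gives 80.5% power. Simulating 10,000 trials with a binomial model adjusted for baseline DI gives 80.0%. The stated 80% is reproduced.

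**Patient level.** One 4-6 to 7-8 conversion changes the DI by -100/n points:

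| Biopsies n | Change in DI | DI category as written |
|---|---|---|
| 6 | -16.7 | response |
| 10 | -10.0 | response |
| 11 | -9.1 | stable |
| 18 | -5.6 | stable |

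**Patient-level label, 6 biopsies.**

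| Case | Numerator | DI change | Mean change | Worst change | Overall |
|---|---|---|---|---|---|
| A: 6,4,1,1,1,1 to 7,4,1,1,1,1 | 4-6 | -16.7 (response) | +0.17 (stable) | +1 (progression) | stable, by the tie rule |
| A | 4-8 | 0 (stable) | +0.17 (stable) | +1 (progression) | stable |
| B: 3,4,1,1,1,1 to 7,4,1,1,1,1 | 4-6 | 0 (stable) | +0.67 (stable) | +3 (progression) | stable |
| B | 4-8 | +16.7 (progression) | +0.67 (stable) | +3 (progression) | progression |

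Changing the numerator corrects case B. It does not correct the label in case A, which needs a separate rule. Not every case is mislabelled: six normal biopsies of which one becomes 7 give mean +1.0 and worst +6, hence progression under either numerator.

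**Arm level.** Each follow-up 7 or 8 understates the arm's DI by 100/(30 x 6) = 0.56 points, and 0.56/11 = 5.1% of the planned difference. With 18 biopsies per patient it is 100/(30 x 18) = 0.19 points.

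The standard error implied by 80% power is 11/(1.96 + 0.84) = 3.93 points, so each excess biopsy in one arm moves z by 0.56/3.93 = 0.14.

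| Assumed excess of 7-8 biopsies in one arm | DI understated by | Shift in z |
|---|---|---|
| 1 | 0.56 | 0.14 |
| 3 | 1.67 | 0.42 |
| 5 | 2.78 | 0.71 |

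Seen another way: if the SF arm had 4 such biopsies among 180 on top of an 11% DI as written, the rate of scores 4-8 would be 11 + 100 x 4/180 = 13.2%, while the DI still read 11%.

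**The case against.** Six points can be made for the plan.

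- **The restriction is open, and the other measures use the full scale.** Section 8.2.1 says the DI looks only at dysplasia. A follow-up 7 always raises the worst score, because baseline cannot exceed 6. So the event is not lost from the trial. But the worst score is secondary, and the primary test still misreads the event.
- **Section 5.6 lists development of cancer as a reason for withdrawal.** A cancer found before month 12 may leave no follow-up DI. This narrows the problem mainly to carcinoma in situ, or to carcinoma first seen at the end-of-treatment bronchoscopy. It does not remove it: section 5.6 does not name carcinoma in situ and gives no DI rule, and section 5.5 schedules the only on-study follow-up bronchoscopy at the end of treatment.
- **The size is unknown.** No frequency is given, patients with normal biopsies are eligible, and similar counts in both arms would largely cancel. This stands.
- **The z shifts are at the upper end.** With an assumed intraclass correlation of 0.2 the design effect is 1 + 5 x 0.2 = 2, and z per biopsy is 0.56/(3.93 x 1.41) = 0.10. With 18 independent biopsies it is 0.19/(3.93/1.73) = 0.08. This also stands.
- **The primary biopsy grouping is not clearly named in section 9.1.** If it is the six standard sites, a re-biopsied lesion elsewhere does not enter the primary DI. A lesion at a standard site does.
- **The patient-level label has no test in section 9.** True, so the second part of the fix matters less than the first.

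**Conclusion.** The definition is wrong as written, and that conclusion needs no assumption about event rates: the plan gives an explicit score range that codes carcinoma in situ and carcinoma at follow-up as absence of dysplasia. The effect on the result is uncertain. Per excess biopsy in one arm it is 0.56 DI points and about 0.14 in z, given 30 completers per arm, 6 independent biopsies each and a placebo DI that stays at 22%. It is smaller with more biopsies or with clustering. A few such biopsies would matter only if they fell unevenly between the arms or the result were near the threshold. The point should be fixed because the endpoint reverses direction at the most serious step on its own scale and the correction is nearly free.

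**What to change.** 1. Define the DI numerator as biopsies scoring 4 or higher (4-8) at both bronchoscopies, in the same words in sections 8.2.1, 8.3.1(c) and 9.1.
2. In the patient-level histologic response (8.2.1 and 8.3.1), state that any post-baseline score of 7 or 8, including one first found at the end-of-treatment bronchoscopy, is classified as progression whatever the 2-of-3 result. This is a rule for coding the endpoint and does not bear on patient care.

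The cost is one phrase in three sections and one sentence in two. Baseline DI values do not change, because scores 7 and 8 are ineligible then, and the stated power assumptions stand. No new data are needed. The change should be made before unblinding.
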